After the consent process, clinicians will go through the interprofessional CST. The CST will occur over the course of 10 hours and will include short didactic sessions around giving bad news, eliciting parental goals, the core competencies of interprofessional collaborative practice⁸⁸, and adaptation for the CICU of the common components of a family meeting as represented in the CHOP Family Meeting Resources (http://intranet.chop.edu/sites/social_work/family-meeting-resources.html). Skills practice groups will include no more than 6 learners at a time. Didactic sessions may be in person or may be performed independently online as needed. Whether in-person or online, sessions may be audio or video recorded. There will be an online survey immediately after the CST to evaluate the clinicians' perception of effectiveness of the course. One month after the completion of the CST, a random sample of 8 participants will take part in a 15-30 minute acceptability interview regarding the CST.

Following the CST, a set of at least 23 actual family meeting encounters with trained clinicians will be audio recorded and coded.

A measure of team function will be assessed pre and post-CST by comparing the amount of time different members of the clinical team speak, and the kind of input offered by members of different disciplines within the team for simulated and actual family meetings. Team member perception and satisfaction with collaboration will be measured after their participation in clinical encounters both pre and post-CST by administering the modified Baggs CSACD-N tool to all clinician team members who participate in an actual encounter. This tool will capture each discipline's experience with collaboration with other team members and satisfaction with care decisions. Finally, fidelity of clinician behavior to the intended intervention in post-intervention family meetings will be determined by a fidelity checklist.

Actual meetings will each last 30-120 minutes. Clinicians participating in the intervention will be enrolled for the entirety of the study, lasting up to four years. They will have at least 21 points of contact with the research team, but some clinicians may participate more frequently due to the unknown composition of the observed actual family meetings.

Clinicians Not Participating in Intervention

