3.1.4 CST Intervention

After the pre-intervention phase, clinicians participating in the intervention will go through the interprofessional CST. The CST will occur over the course of 10 hours and will include short didactic sessions around giving bad news, eliciting parental goals, the core competencies of interprofessional collaborative practice, and the common components of a family meeting. Didactic sessions may be in person or may be performed independently online as needed. Whether in-person or online, sessions may be audio or video recorded. Clinicians must complete all parts of the CST training in order to continue to be enrolled in the study. Supplemental handouts that will be used in the training are available in Appendix 11.3. After completion of the intervention, clinicians who participate in the training will be given a course evaluation to determine clinicians' perception of the usefulness and satisfaction with CST. They will be asked to rate their level of agreement with aspects of the course on a 5 point Likert-type scale. Post-intervention survey will also include clinician burnout measures, demographics, and changes in family meeting communication since the onset of the COVID-19 pandemic. One month after completion of the CST training, a random sample of 8 participating clinicians will complete a 15-30 minute acceptability interview regarding the CST training.

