5 STUDY EVALUATIONS AND MEASUREMENTS

5.1 Screening and Monitoring Evaluations and Measurements

5.1.1 Evaluations, Measures

Measures for Co-Design

- Follow-Up focus group (See Appendix 11.5 for focus group guide)
- Post-focus group survey (See Appendix 11.6 for survey)
 - *Demographics of co-design participants*: The following baseline data will be collected: role in the co-design, gender, race, and ethnicity.
 - *Perception of co-design process and level of engagement*: Modified version of “Coalition Effectiveness Inventory”¹¹⁰⁻¹¹² that consists of one 14-item section measuring participants’ perceptions of the Co-design leader’s effectiveness and one 10-item section measuring participants’ perceptions of their own involvement and commitment to the Co-design process.

Measures for Post-Intervention

- *Course Evaluation - Satisfaction with CST and perception of skill usefulness*: This course evaluation is designed to determine clinicians’ perception of usefulness and satisfaction with the CST program. They will be asked to rate their level of agreement with aspects of the course on a 5 point Likert-type scale. Furthermore, the current burnout rate of clinicians will be assessed using the Maslach burnout score.¹⁰³ Additionally, changes that CICU clinicians have implemented regarding family meetings due to the 2020 COVID-19 pandemic will be recorded. Finally, clinician demographics will be collected including role in CICU, gender, race, and ethnicity. See Appendix 11.11 for complete course evaluation, Maslach burnout score, and COVID Change in Practice survey
- *Intervention fidelity checklist*: The Fidelity Checklist is a list of 7 behaviors of clinicians used to determine if clinicians used the tools and documents taught in the intervention. See Appendix 11.12 for the Intervention Fidelity Checklist
- *Acceptability Interview - 1 month follow-up*: We will do a semi-structured interview with clinicians reviewing their experience of the intervention process including what worked well and what they would recommend changing. Emphasis will be placed on virtual aspects of the training given the novelty of the implementation due to the COVID-19 pandemic. The semi-structured interview guide is in Appendix 11.13

Surveys for Clinicians Participating in Actual Family Meetings

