Team function will be analyzed for simulated family meetings by comparing the change in the number of minutes that clinicians from each discipline speak in pre and post-CST meetings using linear regression and controlling for the length of the meetings.

To assess the impact of the CST program in actual family meetings, audio recordings from actual family meetings will be coded and compared to coded audio recordings from pre-intervention actual family meetings. Since there are generally at least 2 clinicians in each team encounter, we will examine the individual skill acquisition within each part of the team encounter. Within each discipline, there are several clinicians involved in multiple team meetings. We will use fixed-effects regression with a clinician identifier variable as a covariate so that we can examine the effect of CST intervention on skill acquisition, adjusting for the effects of individual clinicians.

Team function will be analyzed in the same way as in simulated meetings by comparing the change in the number of minutes that clinicians from each discipline speak in pre and post-CST meetings using linear regression and controlling for the length of the meetings.

The difference in team member perception and satisfaction with collaboration will be measured after their participation in clinical encounters both pre and post-CST by administering the modified Baggs CSACD-N tool to all clinician team members who participate in an actual encounter. This tool will capture each discipline's experience with collaboration with other team members and satisfaction with care decisions. Means and standard deviations will be calculated for the tool and t-tests will determine if there are significant differences for each discipline pre and post-CST.

Hypotheses will be tested using logistic regression modeling with significance of the two-tailed hypothesis tests set at alpha equal to 0.05.

Clinician perception of the usefulness of CST and satisfaction with the training will be identified by descriptive statistics and differences in the mean and median scores will be calculated to determine retention in perceptions of usefulness one month after the training.

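### The one-month retention analysis of perceived usefulness has no second score: the usefulness survey is given once, and the only one-month contact is an interview with 8 clinicians

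*Protocol*

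**What the plan says.** Section 6.3.2 of the protocol (Efficacy Analysis) covers clinician perception of usefulness and satisfaction with descriptive statistics and adds that "differences in the mean and median scores will be calculated to determine retention in perceptions of usefulness one month after the training". Section 6.2 also lists differences in means and medians for these two outcomes among the secondary endpoints.

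On data collection, section 3.1 states: "There will be an online survey immediately after the CST to evaluate the clinicians' perception of effectiveness of the course". Section 3.1.4 places the instrument at the same point: "After completion of the intervention, clinicians who participate in the training will be given a course evaluation to determine clinicians' perception of the usefulness". Section 5.1.1 gives its format: "They will be asked to rate their level of agreement with aspects of the course on a 5 point Likert-type scale".

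For the one-month point, section 3.1.4 says: "One month after completion of the CST training, a random sample of 8 participating clinicians will complete a 15-30 minute acceptability interview". Section 5.1.1 describes the content of that contact: "We will do a semi-structured interview with clinicians reviewing their experience of the intervention process including what worked well and what they would recommend changing".

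SAP Aim 2(a) plans grounded-theory analysis of the acceptability interview transcripts and descriptive statistics for the acceptability survey. It mentions no change over time.

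**The concern.** Retention is a comparison of a score at the end of training with the same score a month later. The plan commits to that comparison, but the described procedures supply only the first of the two measurements. The one-month contact is a conversation about experience with a subset of clinicians, and nothing in the text says that it is scored.

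Perceived usefulness and satisfaction are secondary endpoints, and clinician acceptability is a stated objective. If the plan is followed, a prespecified analysis will either go unreported or be replaced by something devised afterwards from 8 interviews. Neither supports a statement about whether clinicians still value the training a month later.

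**Working it through.** The documents give no sample size, power or SD for this analysis, so there is no figure to reproduce. The check compares what the analysis needs with what is collected.

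**What the analysis needs.** Two scored administrations of the usefulness items, one at the end of training and one a month later (section 6.3.2).

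**Where the usefulness score is collected.**
- Section 3.1: one online survey immediately after the CST.
- Section 3.1.4: course evaluation after completion of the intervention.
- Section 4.4.1: the survey is listed with the training visits.
- Sections 5.1.1 and 5.2.1: the same evaluation is described, with no repeat.
- Table 1: marked once, in the intervention phase.

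Scheduled time points with a usefulness score: 1.

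**What happens at one month.**
- Sections 3.1, 3.1.4 and 5.2.1: an interview of a random sample of 8 clinicians. Section 4.5.2 lists the same interview.
- Section 5.1.1: the interview is semi-structured.
- Clinician Schedule of Evaluations (section 5.1.1): the interview is the only item labelled one month.
- SAP Aim 2(a): acceptability transcripts are analysed qualitatively.

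Scheduled one-month usefulness scores: 0. Paired scores: 0.

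**Could another instrument supply the second score?**
- The survey after actual family meetings (sections 3.1.5 and 4.5.1) measures perceived team function and collaboration with the CSACD-N, not usefulness of the training. It is timed by meetings, not by months since training.
- The acceptability satisfaction survey named in section 6.2 has no stated timing, and its reference (120) is the one attached to the parent worksheet survey in sections 5.1.1 and 6.2.
- The appendix list in the table of contents shows one post-intervention survey (11.11) and one clinician acceptability interview guide (11.13). No separate one-month survey is listed.

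**Illustrative precision if scores were collected.** With complete pairs, the 95% CI half-width for a mean paired change, in units of the SD of the change, is t(0.975, n − 1)/√n.
- n = 8: 2.365/√8 = 0.836 SD.
- n = 20: 2.093/√20 = 0.468 SD.

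The interviewed sample is 8/20 = 40% of the minimum enrolment, and a smaller share if more than 20 clinicians are trained.

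**The case against.** The strongest counter-argument has four parts.

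1. **The SAP does not carry the retention analysis forward.** The sentence in section 6.3.2 may be a leftover, and the SAP already says that interviews are handled qualitatively. This makes improvised scoring less likely. But the SAP does not withdraw the protocol's commitment, so the two documents still differ.

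2. **The interview guide and the course evaluation (Appendices 11.13 and 11.11) are not in the text available for review.** A rating item inside the interview therefore cannot be ruled out. This stands as a limit on certainty. Even so, such an item would reach only 8 of at least 20 clinicians, and the body of the protocol describes none.

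3. **The schedule tables are weak evidence on timing.** In the Clinician Schedule of Evaluations, the course evaluation and the one-month interview share a single post-CST column. Table 1 gives the survey a window of study days 2-200. That is fair. The timing rests on the prose of sections 3.1 and 3.1.4, which is clear.

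4. **The effect is narrow.** End-of-training usefulness and satisfaction remain fully describable. The retention comparison has no hypothesis, threshold or power statement and is not named among the endpoints in section 2.2. The primary endpoint is qualitative. This stands too, and it keeps the point at moderate weight.

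**Conclusion.** The concern holds. As described, the protocol collects usefulness scores at one time point and none at one month, so the promised difference in means and medians cannot be calculated. This is a conflict between a stated analysis and the data schedule, not a missing detail. It affects one secondary sub-analysis and no other result.

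The conclusion assumes that the unseen appendices add no scored one-month measure. If the interview guide did contain ratings, the comparison would rest on 8 clinicians, with a half-width of about 0.84 SD. The half-widths are illustrative: they assume complete pairs, are expressed in an SD that the documents do not give, and for the larger group take the enrolment minimum of 20.

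**What to change.** Choose one of two changes.

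- **Keep the analysis.** Resend the same 5-point usefulness and satisfaction items through REDCap one month after training to all trained clinicians, not only the 8 interviewed. Add this administration to Table 1, the Clinician Schedule of Evaluations and sections 3.1.4, 4.5 and 5.1.1. In section 6.3.2 and the SAP, specify the within-clinician change with a 95% CI and the number of complete pairs. Responses already carry a participant-linked number (section 8.2), so pairing is feasible. The cost is one short extra survey for about 20 clinicians who are already enrolled and contacted by email.
- **Drop the analysis.** Delete the retention clause from section 6.3.2, align the wording on differences in section 6.2, and report end-of-training scores descriptively with the one-month interviews analysed qualitatively, as SAP Aim 2(a) already plans. The cost is a wording edit. This option remains open if training has already finished.

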6.4 Sample Size and Power

We hypothesize that the CST will change clinician behavior by increasing the number of skills demonstrated in a simulated family meeting. Sample size calculations using existing data about acquisition of skills being evaluated in the CST²⁹ demonstrated that a total of 20

clinicians will be needed to identify significant changes in the following skill outcomes: discussing the big picture, responding to emotion, and performing several empathetic verbal skills using 80% power and an alpha=0.05.

Sample size calculations for determining change in clinician skill acquisition by discipline requires that there be an adequate number of actual encounters recorded such that they can be analyzed by provider type. Sample size calculations for simulated family meetings apply here as well in that we will need to have at least 20 team encounters pre and post-CST intervention to be able to look at the change in outcome before and after the intervention. Since there are generally at least 2 clinicians in each team encounter, we will examine the individual skill acquisition within each part of the team encounter. Within each discipline, there are several clinicians involved in multiple team meetings. We will use fixed-effects regression with a clinician identifier variable as a covariate so that we can examine the effect of CST intervention on skill acquisition, adjusting for the effects of individual clinicians.

Team function will be analyzed by comparing the change in the number of minutes that clinicians from each discipline speak in pre and post-CST meetings using linear regression and controlling for the length of the meetings. Sample size calculations based on previous data⁸⁷ and assuming 80% power and an alpha=0.05 will only require 3 paired respondents pre and post-CST to identify significant differences.

A sample size of 130 parent-patient dyads for the survey and 30 parent-patient dyads for the interview is based on using CONSORT recommendations for pilot study sample size calculations. We calculated the parent-patient dyad sample size by estimating the required sample size for the future stepped wedge study using the Hospital Anxiety and Depression Scale (HADS) as the primary outcome for parents, as HADS is a frequently used outcome in palliative care research with well-established psychometric properties.^{129,130} We will assume a one sided 80% CI for the effect size of 0.1 times the SD, to exclude the minimum clinically important difference if the null hypothesis is true.¹³¹ The minimally important difference is a change of 2 on the HADS scale. The estimated sample size for the main study would be 286. For the pilot study, we estimated the number of participants required as around 30% of the number required for the main Phase 3 trial therefore, we aim to enroll a total of 46 parent-patient dyads pre and post the intervention. In previous studies enrolling parents and children with serious illness, our approach-to-enrollment rate was above 50%. Assuming 45% or more of parent-patient dyads approached will enroll and there are 150 eligible patients per year, we will need to approach approximately 350 parent-patient dyads to enroll 130 evaluable parent-patient dyads for the survey and 30 evaluable parent-patient dyads for the interview prior to the intervention. We have allotted 24 months to enroll 46 evaluable parent-patient dyads for the survey and 20 evaluable parent-patient dyads for the interview pre-intervention.

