2.2 Secondary Objectives (or Aim)

The secondary objectives are to:

- Evaluate CICU clinicians' perceived feasibility and acceptability with the CST
- Evaluate CST impact on communication skills and team function in the actual family meeting
- Evaluate clinicians' burnout rates and changes that CICU clinicians have implemented regarding family meetings due to the 2020 COVID-19 pandemic
- Evaluate the fidelity of clinician behavior to the intended intervention
- Learn about parents perspectives about communication challenge
- Learn about parental acceptability about parent-facing intervention elements including preparation for family meetings in the CICU and the written summary received after the family meeting

The following secondary endpoints will be used to assess CICU clinicians' perceived feasibility and acceptability with CST:

- Perceived acceptability of CST
- Metrics of enrollment rates and missing data
- Post-CST clinician survey
- Acceptability interview carried out with randomized subset of 8 intervention participants.

The following secondary endpoints will be used to assess CST impact on clinician behavior in simulated family meetings:

- Communication skill acquisition
- Team collaboration

The following secondary endpoints will be used to assess CICU clinicians' burnout rate and changes that CICU clinicians have implemented regarding family meetings due to the 2020 COVID-19 pandemic:

- Maslach burnout score¹⁰³
- COVID change in practice survey

The following secondary endpoints will be used to assess CST impact on clinician behavior in actual family meetings:

- Communication skill acquisition
- Team collaboration
- Team member perception and satisfaction with collaboration
- Fidelity of clinician behavior to intervention

The following secondary endpoints will be used to assess parents' perspectives about communication challenges in the CICU:

- Satisfaction feelings when communicating with the clinical team with decision-making
- Understanding of patient's medical condition
- Trust in medical team
- Levels of anxiety, depression, and post-traumatic stress

The following secondary endpoints will be used to assess parents' acceptability of the parent-facing elements of the intervention; including preparing for the meeting and their perception of the written summary after the family meeting

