4.4.1 Clinicians Participating in Intervention: Visit 2-11

- Administration of CST program over the course of 10 hours. Sessions may be audio or video recorded.
- Administration of online course evaluation survey, burnout scale, demographics, and communication in family meetings since COVID-19 pandemic

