- Specialty notes related to CICU family meeting
- CICU Summary Worksheet

Interviews for Parent-patient Dyads in the Pre-Intervention

- The interviews will cover parents' experiences in family meetings and perspectives on communication with the clinical team. (See interview guide under Appendix 11.16)

Interviews for Parent-patient Dyads in the Post-Intervention

- The interviews will assess parents' acceptability of the parent-facing elements of the intervention, including preparing for the meeting and their perception of the written summary after the family meeting. (See interview guide under Appendix 11.17).

Quantitative Coding of Audio Recordings of Actual Family Meetings

- *Modified VitalTalk coding scheme named SCOPE*^{29,121,122}: The small number of new codes added will measure engagement by the attending physician or team members from other disciplines, and adherence to elements of best practices in family meetings (e.g., facilitating introductions of participants, setting an agenda, and summarizing what was discussed in the meeting). Coders will be trained in the coding scheme using a manual with detailed definitions of all the codes.
- *Medical Interaction Process System (MIPS)*⁸⁰: MIPS is a previously validated coding scheme with good psychometric properties that was developed for training clinicians in communication and related research⁸⁰. It has been used extensively in communication analysis^{83,123}. MIPS draws upon a patient-centered approach and codes individual utterances between providers and patients allowing for coding of both content and affective information.
- *Time each member speaks during meeting*: Team function will be analyzed by comparing the change in the number of minutes clinicians from each discipline speak in pre and post-CST meetings using linear regression and controlling for the length of the meetings.
- *Performance Assessment for Communication and Teamwork (PACT-Novice)*^{124,125}: The PACT Tool Set was developed to assess performance on team work and communication and builds upon the framework of TeamSTEPPS, a widely used system designed to improve patient safety, communication, and teamwork skills among health care professionals. The PACT-Novice tool will allow us to quickly train study staff to evaluate teamwork and communication behaviors.

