- *Bruce et al. Evaluation Tool*¹²⁶: This novel evaluation tool was recently developed to assess family meetings, including clinician skills, team function, meeting leadership, and other elements of successful family meetings.

Clinician Schedule of Evaluations
--

Diagnostics/Measures	Co-design	Pre-CST Actual Meetings	Post-CST Evaluation	Post-CST Actual Meetings
Focus Group	X			
Focus Group Survey	X			
Course Evaluation including Maslach burnout score and COVID-19 questions, demographics.			X	
1 Month Follow-Up Acceptability Interview			X	
Demographics		X		X
CSADC-N		X		X
SCOPE		X		X
MIPS		X		X
PACT-Novice		X		X
Bruce et al. Evaluation Tool		X		X
Time each member speaks		X		X

Qualitative Coding of actual family meetings

- Using a grounded theory, audio recordings will also be coded by 2 coders for thematic content to better understand team functioning and collaboration
- Video recordings will be used for speaker attribution in the coding phase.

Qualitative Coding of parent-patient dyad interviews

- Using a grounded theory, audio recordings will also be coded by 2 coders for thematic content to better understand parental experiences communicating with the medical team in the CICU.

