6.3.2 Efficacy Analysis

Qualitative analysis of focus groups conducted during the co-design session will identify themes for elements of the training that may need to be modified.

To evaluate the reliability and validity of the coding scheme, audio recordings from simulated family meetings will be coded and compared to coded audio recordings from pre-intervention simulated family meetings. Inter-rater reliability will be confirmed by having a random sample of 10% of the audio files coded twice by different coders. Only codes with K statistic greater than 0.6 will be included in the final analysis. Convergent validity of the revised coding scheme will be assessed by computing the correlations between the revised VitalTalk coding scheme and the comparable content categories of the MIPS. For this, audio files will be coded using both coding systems and spearman rank correlations will be calculated between the two systems. Coefficients greater than 0.50 will indicate a good level of concurrence between the behaviors measured by the two interaction systems. To evaluate if there are differences in clinician behavior pre and post-CST, coders will be blinded to whether an audio file was made prior to or after CST, and whether it was in a simulated or actual clinical encounter by playing files in a random order.

To evaluate differences in individual skills acquired (SPIKES, NURSE, interprofessional competencies) in simulated family meetings, we will use the McNemar test to compare the proportion of subjects possessing a skill pre-CST in simulated encounters with the proportion who possessed the skill after CST. Each skill will be analyzed separately. The comparison will be made for each behavior assessed and each clinician discipline that demonstrates the behavior. We will also estimate the probability that a participant who did not demonstrate a skill in the pre-CST would demonstrate that skill in the post-CST as a simple ratio. We will estimate 95% confidence intervals using standard techniques. We will also use paired t-tests to examine if there is a difference in skill acquisition (using the continuous version of each of the skill outcomes) between the pre- and post-CST intervention and Wilcoxon signed rank tests.

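### The skill tests and the 80% power at 20 clinicians belong to simulated family meetings that no visit schedules, and the 20 is reused for actual meetings without a calculation

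*Protocol*

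**What the plan says.** **Where simulated meetings are analysed.** Protocol 2.2 opens a list of endpoints with "The following secondary endpoints will be used to assess CST impact on clinician behavior in simulated family meetings". Section 6.4 states the hypothesis in that setting ("We hypothesize that the CST will change clinician behavior by increasing the number of skills demonstrated in a simulated family meeting") and concludes that 20 clinicians give 80% power at alpha 0.05. Section 6.3.2 says "we will use the McNemar test to compare the proportion of subjects possessing a skill pre-CST in simulated encounters" and adds paired t and Wilcoxon signed-rank tests. It also uses simulated recordings for coding reliability and for speaking time.

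**What is collected.** Section 5.1.1 lists the coding tools under "Quantitative Coding of Audio Recordings of Actual Family Meetings". The Clinician Schedule of Evaluations places SCOPE, MIPS, PACT-Novice, the family-meeting evaluation tool and speaking time under "Pre-CST Actual Meetings" and the matching post-training column. Sections 4.3 and 4.5 say skills are assessed in actual encounters. For the training visits, 4.4.1 says "Administration of CST program over the course of 10 hours. Sessions may be audio or video recorded" and otherwise lists only the course evaluation survey.

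**How the 20 reaches actual meetings.** Section 6.4: "Sample size calculations for simulated family meetings apply here as well in that we will need to have at least 20 team encounters" before and after training. The analysis named there is regression with a clinician identifier as a fixed effect.

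**The SAP.** It has no simulated analysis. It compares actual meetings before and after with two-sample tests, and speaking time with a regression adjusted for meeting length. Mixed models follow only if sample size and univariate results allow. Aim 2(c) gives target changes (60%, 40% and 30%) and 230 meetings per period, with no power statement.

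**The concern.** A power statement should belong to a comparison that the study will make. Here the test, unit and setting of the powered comparison (paired, clinician, simulated) all differ from those of the data scheduled (recorded actual meetings, before and after). Someone reading 6.4 would take the skill comparison as powered at 80%, and no such figure exists for it. A null result in actual meetings would then be hard to interpret, because nothing says what difference the design could have shown.

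Two linked inconsistencies affect any restatement: how many meetings are recorded per period, and whether the clinicians who are trained are recorded before training. The second decides whether a clinician fixed-effects model can estimate the effect of training an individual. If no trainee is observed before training, training status never varies within a clinician.

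**Working it through.** **1. Can the 20 be reproduced?** No. Section 6.4 cites existing data but gives no pre/post rates, discordant proportions, mean change or SD. Working backwards, a paired t-test with 20 pairs, two-sided 5% and 80% power, detects 0.66 SD of the within-clinician differences. Whether that lies behind the 20 is not stated.

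**2. Simulated assessments scheduled.** Table 1, the visit lists in 4.1 to 4.5 and the Clinician Schedule of Evaluations contain co-design, training, course evaluation, acceptability interview and actual meetings. Pre/post simulated assessments: 0.

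**3. What the actual-meeting comparison could show** if meetings are independent and unpaired (two-sample t-test, two-sided 5%, 80% power). The CI half-width is t(0.975, 2n−2) × √(2/n). The binary half-width assumes a skill rate near 50%: 1.96 × √(0.5/n).

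| Meetings per period | Detectable difference (SD) | 95% CI half-width (SD) | Binary half-width |
|---|---|---|---|
| 20 | 0.91 | 0.64 | 31 points |
| 23 | 0.84 | 0.59 | 29 points |
| 28 | 0.76 | 0.54 | 26 points |

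These SDs are of the outcome, so they cannot be set directly against the 0.66 in step 1.

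**4. Does moving from paired to unpaired lower the power?** It depends on inputs the protocol does not give.
- Continuous outcome: the paired effect converts to d = 0.66 × √(2(1−ρ)). At 20 vs 20 this gives 82%, 67%, 53% and 35% power for assumed within-clinician correlations ρ of 0, 0.3, 0.5 and 0.7.
- Binary outcome: for an assumed rise from 20% to 60% with 5% of clinicians losing the skill, exact McNemar with 20 pairs has 69% power. Twenty vs 20 unpaired has 75%.

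**5. Clustering at 23 vs 23** (assumed ICC 0.05 to 0.20).
- Each clinician in one period only, 2 to 4 observations each: the design effect 1+(m−1)×ICC runs from 1.05 to 1.60. The effective n per period is 23/1.05 = 21.9 down to 23/1.60 = 14.4, and the detectable difference is 0.87 to 1.08 SD.
- Clinicians balanced across both periods: the variance of the difference is multiplied by (1−ICC), so 0.845 × √0.95 = 0.82 and 0.845 × √0.80 = 0.76 SD.

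**6. Meeting counts.** Section 6.4 sets a floor of 20 before and after. Section 3.1.5 wants 23 per discipline after training, from about 28 recorded, which meets the floor. Section 3.3.2 says 56 per discipline; this may be 28 + 28, but the text does not say so. The SAP says 230 per period. For the post period, 8.5 caps enrolment at 50 dyads and Table 1 and 4.5.5 give one recording visit each: 230/50 = 4.6 recordings per dyad at least, against 1 scheduled.

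**7. Who is recorded before training.** Table 1, 3.1.3 and 4.3.1 list only clinicians not taking part in the intervention. The preamble of 4.3 says trainees' skills are assessed in actual encounters before they are trained, and that both groups take part. Section 8.5 selects meetings with at least two intervention clinicians and does not limit this to one period.

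**The case against.** The strongest defence is that this is leftover text. The SAP has dropped simulation, calls the work a pilot test, and its tests can run on actual meetings. The primary endpoint is qualitative (6.1). Formal power for a pilot's secondary outcomes is partly a matter of preference. All of that stands and limits the seriousness, but the current protocol still states 80% power for a comparison with no scheduled data.

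A second defence is that actor-based practice takes place inside the training and may be recorded. That does not supply the data: no skill measure is scheduled on those sessions, and there is no pre-training baseline.

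A third is that the change of unit has a reason: 6.4 wants enough encounters to analyse by provider type. That may explain why clinicians became encounters, but it is not a calculation.

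Some stronger readings are tempting and should be resisted. A reader might infer that 20 is too few, or that correct power must be lower; steps 4 and 5 show that the direction depends on unstated inputs. A reader might see four conflicting meeting counts, but 20, 23 and 28 fit together. The dyad cap tests 230 only for the post period, because pre-training families receive an information sheet and may opt out (8.6.1). A reader might also conclude that the small paired number given for speaking time in 6.4 is wrong; its basis is not shown, and nothing in the documents shows it to be wrong.

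**Conclusion.** The point holds. The paired skill tests and the 80% power at 20 clinicians refer to pre/post simulated meetings that are not scheduled. The 20 is applied to actual meetings by assertion, so the comparison the study can make has no power or precision statement. That absence can be read directly from the documents. The sizes in steps 3 to 5 are illustrations under stated assumptions (independence, a 50% rate, ICC, observations per clinician), not estimates of this study's true power.

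The linked points are genuine but narrower. The 56 and the 230 are not reconciled with the 23-from-28 target. The documents are mixed on whether trainees are recorded before training, and the limit on the fixed-effects model applies only if they are not. Because these are secondary endpoints and the SAP's tests can still run, this should be fixed but does not threaten the study.

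**What to change.** - Delete the simulated-meeting tests and their power statement from 6.3.2 and 6.4, and the matching wording in the Abstract, 1.3, 2.2, 3.1, 5.2.1 and 6.2. Rest the coding-reliability step in 6.3.2 on recordings that will exist.
- Replace the reused 20 with a detectable difference or 95% CI precision for the actual-meeting pre/post comparison, at one reconciled meeting count per period. The table in step 3 shows the form.
- State the clustering assumption, including whether clinicians are expected in one period or both, since this decides whether the figures widen or narrow.
- Reconcile 56 per discipline and 230 per period with the 23-from-28 target, checking 230 against the 50-dyad cap and the single recording visit.
- State whether trainees are recorded before training, and align Table 1, 3.1.3 and 4.3.1 with the 4.3 preamble. If they are not, do not present the clinician fixed-effects model as the effect of individual training; describe the result as a meeting-level pre/post comparison.

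Cost: wording and one recalculation, with no new procedures, consent or participants. The restated figure may be less favourable than 80% at 20. Keeping the simulated analyses would instead mean scheduling those assessments, which adds study visits.
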